5.4 Contraception

It is not known if pembrolizumab has adverse effects on a fetus *in utero* nor if there are transient adverse effects on the composition of sperm. Non-pregnant, non-breast-feeding women may be enrolled if they are willing to use 2 methods of birth control or are considered highly unlikely to conceive. Highly unlikely to conceive is defined as 1) surgically sterilized, or 2) postmenopausal (a woman who is ≥ 45 years of age and has not had menses for greater than 1 year will be considered postmenopausal), or 3) not heterosexually active for the duration of the study. The two birth control methods can be either two barrier methods or a barrier method plus a hormonal method to prevent pregnancy. Subjects should start using birth control from time of informed consent throughout the study period and up to 120 days after the last dose of study drug.

The following are considered adequate barrier methods of contraception: diaphragm, condom (by the partner), copper intrauterine device, sponge, or spermicide. Appropriate hormonal contraceptives will include any registered and marketed contraceptive agent that contains an estrogen and/or a progestational agent (including oral, subcutaneous, intrauterine, or intramuscular agents).

Subjects should be informed that taking the study medication may involve unknown risks to the fetus (unborn baby) if pregnancy were to occur during the study. To participate in the study, they must adhere to the contraception requirements described above for the duration of the study and 120 days following the last dose of study drug. If there is any question that a subject will not reliably comply with the requirements for contraception, that subject should not be entered into the study.

Male subjects who are not surgically sterile (vasectomy) must agree to use an adequate method of contraception. Male subjects with female sexual partners who are pregnant, possibly pregnant or who could become pregnant during the study must agree to use condoms from the time of informed consent through 120 days after the last dose of study therapy. Total abstinence for the same study period is an acceptable alternative.

5.5 Use in Pregnancy

If a subject inadvertently becomes pregnant while on study treatment, the subject will immediately be removed from the study. The site will contact the subject at least monthly and document the subject's status until the pregnancy has been completed or terminated. The outcome of the pregnancy will be reported to Hoosier Cancer Research Network (HCRN) **within 1 business day** if the outcome is a serious adverse experience (e.g., death, abortion, congenital anomaly, or other disabling or life-threatening complication to the mother or newborn). HCRN will report this information **within 1 business day** to Prometheus. The study investigator will make every effort to obtain permission to follow the outcome of the pregnancy and report the

condition of the fetus or newborn to HCRN. If a male subject impregnates his female partner, he must immediately inform the site study personnel and the pregnancy reported and followed as described above.

5.6 Breastfeeding

It is unknown whether pembrolizumab or IL-2 is excreted in human milk. Since many drugs are excreted in human milk, and because of the potential for serious adverse reactions in the nursing infant, subjects who are breast-feeding are not eligible for enrollment.

6. TOXICITIES AND DOSE DELAYS/DOSE MODIFICATIONS

The NCI Common Terminology Criteria for Adverse Events (CTCAE) v4.03 will be used to grade adverse events.

Subjects enrolled in this study will be evaluated clinically and with standard laboratory tests before and at regular intervals during their participation in this study as specified in Study Calendar & Evaluations.

Subjects will be evaluated for adverse events (all grades), serious adverse events, and adverse events requiring study drug interruption or discontinuation as specified in Study Calendar & Evaluations.

6.1 Dose Delays for Pembrolizumab Administration

6.1.1 Start of a New Cycle

A new treatment cycle will only be initiated when all of the following conditions are met:

- ANC $\geq 1,500 \times 10^9/L$
- platelets $\geq 100 \times 10^9/L$
- Non-hematologic treatment related toxicities have improved to \leq Grade 1 or to the subject's baseline values (except alopecia)

If blood counts (first two bullet points above) are below this threshold, blood work is to be repeated weekly until counts are at an acceptable level. If treatment is unable to restart within 12 weeks of the planned treatment date, the subject will be permanently discontinued from study therapy.

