5.1 Pembrolizumab Administration

Subjects will receive 200 mg pembrolizumab every 3 weeks for two cycles. Cycle length is 21 days (i.e., 3 weeks). On the last day of Cycle 2 (+ 3 days), disease status will be assessed via imaging. Following the pembrolizumab treatment, HD IL-2 treatment will commence.

Correlative research analyses during pembrolizumab administration include examining the relationship between clinical response at the end of Cycle 2 with PD-L1 expression of the archived diagnostic tumor tissue. Research analyses also include examining the relationship between changes in soluble PD-L1 level and Type 1 T helper cell/Type 2 T helper cell (Th1/Th2) ratios during therapy (assessed after the 2nd dose) relative to baseline and characterization of intestinal microbiome to the best clinical response (RECIST 1.1 criteria) and to treatment outcome.

Drug	Dose	Route	Schedule	Cycle Length
Pembrolizumab	200 mg	Intravenously (IV) over 30 minutes	Day 1 of each cycle	3 weeks (21 days)

¹ A window of - 1 or + 2 days may be applied to all study visits to accommodate observed holidays, inclement weather, scheduling conflicts etc. Date and time of each drug administration should be clearly documented in subject's chart and electronic case report forms (eCRFs).

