6.2 Dose Delays for HD IL-2

6.2.1 Start of New Cycle

A new treatment cycle will only be initiated when all of the following conditions are met:

- ANC $\geq 1,500 \times 10^9/L$
- Platelets $\geq 100 \times 10^9/L$
- Non-hematologic treatment related toxicities have improved to \leq Grade 1 or to the subject's baseline values (except alopecia)

If blood counts are below this threshold (first two bullet points), blood work is to be repeated weekly until counts are at an acceptable level. If treatment is unable to restart within 12 weeks of the planned treatment date, the subject will be permanently discontinued from study therapy.

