6.2 Protocol Therapy Discontinuation

In addition to discontinuation from therapy related to toxicities as outlined above, a subject will also be discontinued from protocol therapy and followed per protocol under the following circumstances outlined below. The reason for discontinuation of protocol therapy will be documented on the electronic case report form (eCRF)

- Documented disease progression
- Site investigator determines a change of therapy would be in the best interest of the subject
- Subject requests to discontinue protocol therapy, whether due to unacceptable toxicity or for other reasons
 - In a subject decides to prematurely discontinue protocol therapy (“refuses treatment”), the subject should be asked if he or she may still be contacted for further scheduled study assessments. The outcome of that discussion should be documented in both the medical records and in the eCRF.
- Female subject becomes pregnant
- HD IL-2 will be discontinued if there is a ≥ 12 -week delay between cycles
- Pembrolizumab will be discontinued if there is a ≥ 12 -week delay between cycles

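### The neutrophil threshold for starting a new cycle (Sections 6.1.1 and 6.2.1) is printed 1,000-fold too high and cannot be met

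*Combined protocol and SAP*

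**What the plan says.** Section 6.1.1 sets the conditions for starting a pembrolizumab cycle: "A new treatment cycle will only be initiated when all of the following conditions are met". The first condition is "ANC $\geq 1,500 \times 10^9/L", the second is "platelets $\geq 100 \times 10^9/L", and the third concerns recovery from non-hematologic toxicity. Section 6.2.1 gives the same list for HD IL-2, with the identical ANC line followed by "Platelets $\geq 100 \times 10^9/L".

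In both sections, counts below threshold are rechecked weekly, and the delay has a limit: "If treatment is unable to restart within 12 weeks of the planned treatment date, the subject will be permanently discontinued from study therapy". The section headed Protocol Therapy Discontinuation (also numbered 6.2) adds a 12-week limit on the delay between cycles for each drug, in the items beginning "Pembrolizumab will be discontinued if there is a" and "HD IL-2 will be discontinued if there is a".

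The planned treatment is four cycles. Section 5.1 states: "Subjects will receive 200 mg pembrolizumab every 3 weeks for two cycles". Section 5.2 then plans two cycles of HD IL-2 once pembrolizumab is complete.

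**The concern.** An ANC is ordinarily written either per microlitre, in the thousands, or as a small number times 10^9/L. Here a figure in the thousands carries the 10^9/L unit, so the two conventions appear to have been mixed. The platelet line next to it uses that unit correctly, which makes the mismatch plain.

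This is an operative rule. It decides whether a subject is dosed, and failing it for 12 weeks ends study therapy. As printed it cannot be applied, and neither a site nor a monitor can judge adherence to it. Sites must supply their own number, and the protocol does not tell them which. The only other ANC cut-off is the eligibility floor, which is a different value.

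**Working it through.** **Inputs**

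- New-cycle ANC threshold: 1,500 × 10^9/L (Sections 6.1.1 and 6.2.1).
- New-cycle platelet threshold: 100 × 10^9/L (same two lists).
- Planned cycles: 2 pembrolizumab (Section 5.1) and 2 HD IL-2 (Section 5.2).
- Eligibility ANC: printed as 1,000/L (synopsis and Section 3.1). I assume a micro sign was lost when the PDF was read and take it as 1,000/µL. The finding does not depend on this.

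The threshold is not derived from other figures in the plan, so there is no calculation of the plan's own to reproduce. The check is a unit conversion with 1 L = 10^6 µL.

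**Conversion**

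1. Printed ANC: 1,500 × 10^9/L = 1.5 × 10^12/L, and 1.5 × 10^12 / 10^6 = 1,500,000/µL.
2. The same digits read per microlitre: 1,500/µL × 10^6 µL/L = 1.5 × 10^9/L.
3. Ratio of printed to intended: 1,500 / 1.5 = 1,000.

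**Comparison with neighbouring thresholds**

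4. Platelets: 100 × 10^9/L = 100,000/µL, a sensible threshold in the same unit.
5. Printed ANC relative to platelets: 1,500 / 100 = 15 times. After correction: 1.5 / 100 = 0.015 times.
6. Printed ANC relative to the eligibility ANC, read as 1,000/µL: 1,500,000 / 1,000 = 1,500 times. After correction: 1,500 / 1,000 = 1.5 times.

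**Literal consequence**

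7. Planned cycles: 2 + 2 = 4.
8. If the condition applies from pembrolizumab Cycle 2 onward, Cycle 2 can never start and the 12-week rule ends study therapy after one cycle. Then 1 of 4 cycles is given and 3 of 4 are blocked.
9. If the condition also applies to Cycle 1, 0 of 4 are given.
10. On either reading, 0 of 2 HD IL-2 cycles are given.

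**Could the text mean something else?**

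- *A lost micro sign*, as assumed for the eligibility values, does not rescue this line. Restoring one to 10^9/L would make the threshold a further million-fold larger.
- *A decimal comma* does not fit the document, which uses commas for thousands (600,000 IU/kg in Section 5.2; 9,940 deaths in Section 1.1).
- *A correct value elsewhere* was not found. No other section gives a new-cycle ANC threshold.

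**The case against.** Three points can be made on the other side.

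First, the error could come from reading the PDF. The units of this same parameter already look damaged in the eligibility criteria, and one misread character (a decimal point taken for a comma) would produce the printed value. The two sections are near copies, so a program could have misread both in the same way. This cannot be excluded without the PDF. It is less likely than a drafting slip, because the platelet line directly below reads sensibly both times and the digits are exactly those of a per-microlitre value.

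Second, the replacement value is an inference. The document nowhere prints 1.5 × 10^9/L. On the assumption above, the eligibility floor is 1.0 × 10^9/L, so the corrected threshold would exceed the entry threshold. A subject validly enrolled with an ANC between 1,000 and 1,500/µL could then fail the rule for the next cycle. This stands. It is a reason for the sponsor to confirm the number. It also shows that leaving sites to correct the line themselves is not harmless: at such a count, 1,500/µL and a fallback to 1,000/µL give opposite dosing decisions.

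Third, the literal consequence will not occur. A count of 1.5 million/µL is so implausible that no clinician would stop treatment over it, and the wording about restarting and about delays between cycles suggests that the condition was not meant for Cycle 1. Both remarks are fair. They limit the severity, and they make 1 of 4 the more natural literal reading than 0 of 4, but they do not make the printed threshold right.

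**Conclusion.** The concern holds. The new-cycle ANC threshold is wrong as printed in both sections, by a factor of 1,000 if 1,500/µL was intended. Whatever the intended value, 1,500,000/µL cannot be met.

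The conclusion assumes that the text was read correctly from the PDF. The factor of 1,000 also assumes that the digits 1,500 reflect the intended count per microlitre.

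Severity is minor. The expected practical effect is small because sites would probably apply 1,500/µL. The two-stage design, the endpoints and the analyses are unaffected. It still deserves correction, because the line governs dosing and permanent discontinuation.

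**What to change.** In both Section 6.1.1 and Section 6.2.1, replace the ANC line with: ANC ≥ 1.5 × 10^9/L (1,500/µL). Giving both units prevents a repeat of the slip.

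Before amending, the sponsor should confirm 1,500/µL as the intended value and check it against the eligibility ANC, so that a new-cycle threshold above the entry floor is a deliberate choice.

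The cost is two corrected lines in the next amendment. Sample size, endpoints and analysis do not change.

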17. History of autoimmune disease, including but not limited to myasthenia gravis, myositis, autoimmune hepatitis, systemic lupus erythematosus, rheumatoid arthritis, inflammatory bowel disease, vascular thrombosis associated with anti-phospholipid syndrome, granulomatosis with polyangiitis, Sjögren’s syndrome, Guillain-Barré syndrome, multiple sclerosis, vasculitis, or glomerulonephritis. See Study Procedures Manual (SPM) for a detailed list.
 - Subjects with a history of autoimmune-related hypothyroidism on a stable dose of thyroid replacement hormone may be eligible for this study.
 - Subjects with controlled Type I diabetes mellitus on a stable dose of insulin regimen may be eligible for this study.
 - Subjects with a history of celiac disease may be eligible if controlled with diet.
18. Treatment with any investigational agent within 21 days prior to initiation of study treatment and the subject must have recovered from the acute toxic effects of the regimen.
19. Prior organ transplant including allogeneic transplantation.

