6.1.3 Dose Modification for Toxicity

Adverse events (both non-serious and serious) associated with pembrolizumab exposure may represent an immunologic etiology. These adverse events may occur shortly after the first dose or several months after the last dose of treatment. Pembrolizumab must be withheld for drug-related toxicities and severe or life-threatening AEs as per Table 2 below.

Table 2: Dose Modification and Toxicity Management Guidelines for Immune-related AEs Associated with Pembrolizumab

General instructions:				
Immune-related AEs	Toxicity grade or conditions (CTCAEv4.0)	Action taken to pembrolizumab	irAE management with corticosteroid and/or other therapies	Monitor and follow-up
Pneumonitis	Grade 2	Withhold	
 Administer corticosteroids (initial dose of 1-2 mg/kg prednisone or equivalent) followed by taper 	
 Monitor participants for signs and symptoms of pneumonitis Evaluate participants with suspected pneumonitis with radiographic imaging and initiate corticosteroid treatment Add prophylactic antibiotics for opportunistic infections
	Grade 3 or 4, or recurrent Grade 2	Permanently discontinue		
Diarrhea / Colitis	Grade 2 or 3	Withhold	
 Administer corticosteroids (initial dose of 1-2 mg/kg prednisone or equivalent) followed by taper 	
 Monitor participants for signs and symptoms of enterocolitis (ie, diarrhea, abdominal pain, blood or mucus in stool with or without fever) and of bowel perforation (ie, peritoneal signs and ileus). Participants with \geq Grade 2 diarrhea suspecting colitis should consider GI consultation and performing endoscopy to rule out colitis. Participants with diarrhea/colitis should be advised to drink liberal quantities of clear fluids. If sufficient oral fluid intake is not feasible, fluid and electrolytes should be substituted via IV infusion.
	Grade 4	Permanently discontinue		

AST / ALT elevation or Increased bilirubin	Grade 2	Withhold	
 Administer corticosteroids (initial dose of 0.5- 1 mg/kg prednisone or equivalent) followed by taper 	
 Monitor with liver function tests (consider weekly or more frequently until liver enzyme value returned to baseline or is stable)

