	Grade 3 or 4	Permanently discontinue	
 Administer corticosteroids (initial dose of 1-2 mg/kg prednisone or equivalent) followed by taper 	
Type 1 diabetes mellitus (T1DM) or Hyperglycemia	Newly onset T1DM or Grade 3 or 4 hyperglycemia associated with evidence of β -cell failure	Withhold	
 Initiate insulin replacement therapy for participants with T1DM Administer anti-hyperglycemic in participants with hyperglycemia 	
 Monitor participants for hyperglycemia or other signs and symptoms of diabetes.
Hypophysitis	Grade 2	Withhold	
 Administer corticosteroids and initiate hormonal replacements as clinically indicated. 	
 Monitor for signs and symptoms of hypophysitis (including hypopituitarism and adrenal insufficiency)
	Grade 3 or 4	Withhold or permanently discontinue ¹		
Hyperthyroidism	Grade 2	Continue	
 Treat with non-selective beta-blockers (eg, propranolol) or thionamides as appropriate 	
 Monitor for signs and symptoms of thyroid disorders.
	Grade 3 or 4	Withhold or permanently discontinue ¹		
Hypothyroidism	Grade 2-4	Continue	
 Initiate thyroid replacement hormones (eg, levothyroxine or liothyroinine) per standard of care 	
 Monitor for signs and symptoms of thyroid disorders.
Nephritis and Renal dysfunction	Grade 2	Withhold	
 Administer corticosteroids (prednisone 1-2 mg/kg or equivalent) followed by taper. 	
 Monitor changes of renal function
	Grade 3 or 4	Permanently discontinue		
Myocarditis	Grade 1 or 2	Withhold	
 Based on severity of AE administer corticosteroids 	
 Ensure adequate evaluation to confirm etiology and/or exclude other causes
	Grade 3 or 4	Permanently discontinue		

All other immune-related AEs	Intolerable/persistent Grade 2	Withhold	
 Based on type and severity of AE administer corticosteroids 	
 Ensure adequate evaluation to confirm etiology and/or exclude other causes
	Grade 3	Withhold or discontinue based on the type of event. Events that require discontinuation include and not limited to: Gullain-Barre Syndrome, encephalitis		

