	Grade 4 or recurrent Grade 3	Permanently discontinue		

1. Withhold or permanently discontinue pembrolizumab is at the discretion of the investigator or treating physician.

NOTE:
For participants with Grade 3 or 4 immune-related endocrinopathy where withhold of pembrolizumab is required, pembrolizumab may be resumed when AE resolves to \leq Grade 2 and is controlled with hormonal replacement therapy or achieved metabolic control (in case of T1DM).

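### Section 6.1.1 blocks the second pembrolizumab dose for endocrine events that Table 2 lets continue or resume, and Section 6.2.1 repeats the gate for HD IL-2 with no exception for controlled hypothyroidism

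*Combined protocol and SAP*

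**What the plan says.** **Pembrolizumab gate (Section 6.1.1).** A cycle may start only when every listed condition is met. One of them is that "Non-hematologic treatment related toxicities have improved to" Grade 1 or lower, or to the subject's baseline, alopecia excepted. The section closes with: "If treatment is unable to restart within 12 weeks of the planned treatment date, the subject will be permanently discontinued from study therapy". The section headed Protocol Therapy Discontinuation has its own 12-week delay limit for each drug, so the limit is not confined to low blood counts.

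**Immune-event table (Section 6.1.3, Table 2).** The action column is headed "Action taken to pembrolizumab". It reads *Continue* for Grade 2 hyperthyroidism and for Grade 2–4 hypothyroidism; the management given for the latter is "Initiate thyroid replacement hormones (eg, levothyroxine or liothyroinine) per standard of care". A NOTE under the table covers Grade 3 or 4 immune-related endocrinopathy for which pembrolizumab was withheld. It may be resumed once the event is no worse than "Grade 2 and is controlled with hormonal replacement therapy or achieved metabolic control (in case of T1DM"). Grade 2 hypophysitis and new-onset type 1 diabetes are *Withhold*.

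**HD IL-2 gate (Section 6.2.1).** The same toxicity bullet and the same 12-week limit are repeated, again with alopecia as the only exception.

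**Entry (Section 3.2, item 17).** "Subjects with a history of autoimmune-related hypothyroidism on a stable dose of thyroid replacement hormone may be eligible for this study".

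**The concern.** Two rules in the same chapter govern the same decision and disagree. A subject who develops treatment-related hypothyroidism after the first pembrolizumab dose is told to continue by Table 2 and may not start the next cycle under 6.1.1. Sites that follow one rule and sites that follow the other would treat identical subjects differently.

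For HD IL-2 the same bullet produces an odd asymmetry. A subject who enters with autoimmune hypothyroidism on stable replacement passes 6.2.1 through its baseline clause. A subject who reaches the same state on study, and is still graded 2, does not.

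The primary endpoint is the response rate of the whole sequence. Under Section 12.4 a subject is evaluable after one dose of trial drug and one post-baseline assessment, so a blocked subject can count in the denominator without having received HD IL-2. Section 10.1.5 lists thyroid disorders among the identified risks of pembrolizumab, so the situation is foreseeable.

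**Working it through.** The plan gives no figure on this point. The check sets the rules side by side and then dates the consequence.

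**Step 1. The dose 2 decision.** Section 5.1 plans two pembrolizumab doses, so dose 2 is the only later dose either rule can govern. Take a new, treatment-related event:

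| State at planned dose 2 | Table 2 and NOTE | 6.1.1 read literally | Agree? |
|---|---|---|---|
| Hyperthyroidism, Grade 2 | Continue | Blocked | No |
| Hypothyroidism, Grade 2–4 | Continue | Blocked | No |
| Endocrinopathy withheld at Grade 3–4, now Grade 2 and controlled | May resume | Blocked | No |
| Hypophysitis, Grade 2 | Withhold | Blocked | Yes |
| New type 1 diabetes, not yet controlled | Withhold | Blocked while above Grade 1 | Yes |

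The conflict is confined to the first three rows.

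**Step 2. The HD IL-2 decision.** Table 2 states pembrolizumab actions only, so 6.2.1 stands alone. Hypothyroidism on a stable replacement dose is acceptable at entry. The same state reached on study and still graded 2 is blocked.

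**Step 3. Where each gate would be met.** The Section 7 calendar schedules thyroid tests at screening and at the end of pembrolizumab Cycle 2, with none at dose 2. The 6.1.1 conflict therefore needs an event recognised clinically or by an unscheduled test within the first 21 days. A thyroid event found by scheduled testing on treatment meets the 6.2.1 gate.

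**Step 4. Timing and doses lost.**
- Dose 2 is planned for day 1 + 21 = 22. The 12-week limit is 22 + 84 = day 106.
- The protocol gives no fixed HD IL-2 start day. Assume the day after the end-of-Cycle-2 assessment. That assessment falls on day 42 to 45 (42 + 3), so the start is day 43 to 46 and the limit is 43 + 84 = 127 to 46 + 84 = 130.
- The HD IL-2 course is up to 2 × 14 = 28 doses.
- Blocked at 6.1.1 to the limit: 1 of 2 pembrolizumab doses is lost, and the HD IL-2 course with it because study therapy ends. Blocked at 6.2.1 before the first HD IL-2 cycle: the course is lost.

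**The case against.** **Table 2 is the specific rule.** Section 5.1.2 repeatedly sends the reader to Table 2 for treatment holds, restart timing and permanent discontinuation, including in its thyroid block, and 6.1.3 says pembrolizumab is withheld according to that table. A sensible site would follow it. This is good support for what the sponsor probably meant. It does not lift 6.1.1, whose conditions are cumulative and exclusive and which neither mentions Table 2 nor yields to it.

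**A stricter HD IL-2 gate is reasonable.** Section 10.2.6 reports hypotension in 71% of Proleukin-treated patients, and Sections 5.2 and 5.2.1 defer to outside guidelines and a procedures manual that cannot be seen here. This stands as far as it goes: the sponsor may want the stricter gate, but no text says that it is intended.

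**Regrading may solve it.** If a controlled event is graded 1, both gates open. The CTCAE text is not in the documents, so the point applies only to events still graded 2 or higher.

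**Stronger readings a reader might infer.**
- *That 6.2.1 contradicts Table 2.* It cannot, because Table 2 sets no HD IL-2 action.
- *That all Grade 2 endocrine events are affected.* The *Continue* rows are thyroid only. Grade 2 hypophysitis is withheld, and the NOTE concerns events that were Grade 3–4.
- *That HD IL-2 may start on high-dose steroids because 6.2.1 has no steroid condition.* Exclusion 16 bars systemic steroids above physiologic level, and Section 5.3 carries that into the ongoing trial. The immune-event exemption in 5.3.2 is limited to screening and the pembrolizumab phase.
- *That 6.2.1 opens HD IL-2 to Grade 1 myocarditis, or that silence on whether a pembrolizumab discontinuation also ends HD IL-2 is an error.* Section 10.2.6 calls for clinical evaluation to exclude significant cardiac impairment, and the second matter is a sponsor choice. Both are at most optional clarifications.

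**Conclusion.** The point holds in a limited form. Section 6.1.1 and Table 2 give opposite instructions at dose 2 for Grade 2 hyperthyroidism, Grade 2–4 hypothyroidism, and a formerly Grade 3–4 endocrinopathy now controlled at Grade 2. Section 6.2.1 lacks an exception for controlled hypothyroidism, which sits awkwardly with the entry criteria but contradicts nothing.

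For an affected subject the literal consequence is large: the HD IL-2 course, alone or with half the planned pembrolizumab. How many subjects would be affected cannot be said. The documents give no rate for these events, only one pembrolizumab decision is exposed, and no thyroid test is scheduled at it. No subject count, bias or loss of power is claimed, and nothing here shows that unsafe treatment would occur.

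The conclusion assumes that the event is new, judged treatment-related and still above Grade 1 when the cycle is due, and that sites apply the gate as written.

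**What to change.** 1. **Section 6.1.1:** replace the alopecia exception with *(except alopecia, and endocrine events that Table 2 allows to continue or resume)*. This takes Table 2 as it stands. It does not release Grade 2 hypophysitis, and Table 2's hypothyroidism row stays unchanged.
2. **Section 6.2.1:** add an exception limited to hypothyroidism controlled on a stable dose of thyroid replacement, matching exclusion 17. If the sponsor wants the stricter HD IL-2 gate, say so in one sentence instead. Do not extend the exception to hypophysitis, whose Table 2 row includes monitoring for adrenal insufficiency.

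The cost is amendment wording and its IRB approval, with no extra visits, tests or subjects. The one clinical decision is the second item: adopting the exception means some subjects with Grade 2 hypothyroidism on stable replacement would receive HD IL-2. A subject first found hypothyroid at the end of Cycle 2 would still need to reach a stable dose within the existing 84 days.
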